6.1. Subject Disposition and Withdrawals

Frequency counts and percentages of all subjects who are enrolled but do not take study drug, and subjects who are enrolled and complete the study drug/study or discontinue study drug/study early will be presented. All subjects who discontinue from the study will be identified, and their reason for discontinuation in the study will be reported. The denominators for the percentage calculations will be the number of subjects in the enrolled population.

The following frequencies (number and percentage) will be displayed:

- Subjects in the enrolled population
- Subjects who completed the study
- Subjects who discontinued early overall and by reason

A listing of all study subjects, whether they discontinued the study or not, and the reasons for study discontinuations will be provided for the enrolled population.

6.2. Demographic and Other Baseline Characteristics

Demographic and baseline data will be summarized by means of descriptive statistics: continuous variables as mean, SD, median, minimum, and maximum, and categorical variables as frequencies and percentages, based on the enrolled population. Demographic data will include age, sex, race, ethnicity, reproductive potential, height, body weight, and body mass index (BMI). Baseline characteristics will include number of years since diagnosis of Fabry disease, previous use of enzyme replacement therapy (ERT), and previous and current use of angiotensin-converting enzyme inhibitors, renin inhibitors, and angiotensin receptor blockers. The following calculations will be utilized:

- Age = (ICF date date of birth + 1) / 365.25 and truncated to complete years. Age at entry into this study will be re-calculated based on the date of birth recorded in Study AT1001-020
- Weight (in kg) = weight (in pounds) *0.4536
- Height (in cm) = height (in inches) * 2.54
- BMI (kg/m2) = weight(kg)/[(height(cm)/100)²], where m=meters.
- Number of years since diagnosis of Fabry disease = (ICF date of this study date of diagnosis of Fabry disease + 1) / 365.25 and rounded to 1 decimal.
- For any missing days or months, years will be used for the calculation: Number of years since diagnosis of Fabry disease = (year of ICF date of this study – year of date of diagnosis of Fabry disease)
- For missing years, number of years will be missing.
- A month will be defined as 30 days
- ERT status is defined as ERT naïve at baseline and ERT experienced; ERT status is determined based on the subject's ERT status in Study AT1001-020.

All demographic and baseline characteristic data will also be listed.

6.3. Medical History

A summary table of the number and percentage of subjects for medical history by SOC and PT will be produced for subjects in the enrolled population. Medical history will be sorted alphabetically by SOC and PT within the same SOC using the MedDRA coding dictionary, version 21.0, or later version. For the summary tables, a subject may appear more than once if he/she has more than one medical history coded under different SOC or PT categories. However, the subject will be counted only once in the overall category. A by-subject listing with coded SOC and PT along with eCRF term will also be provided.

6.4. Concomitant Medications

Medications will be classified as prior (started prior to the first dose of study treatment in the 036 study) and concomitant (continued past or started on or after the first dose of study treatment in the 036 study). Medications starting after the last dose of study drug will not be considered as concomitant but will be flagged as post medications on the listing. All concomitant medications will be summarized.

All prior and concomitant medications will be classified using the ATC classification coded terms and preferred drug names from the WHO-DD.

Summaries of prior and concomitant medications will be presented separately in tabular form using the level 4 ATC term as an upper classification level and the preferred drug name as a lower classification level. All medications will be summarized and sorted alphabetically by level 4 ATC term and preferred drug name within a given level 4 ATC term. The summary will consist of the frequency and percentage of subjects in the enrolled population who used the medication at least once.

For each subject, the medication will be counted only once within a level 4 ATC term and only once under a given preferred drug name. A subject may appear more than once if he/she has more than one concomitant medication coded under different ATC terms or preferred drug names; however, the subject will be counted only once in the overall category.

A by-subject listing with coded terms will also be provided along with calculated study day.

7. Efficacy

Observed values and changes from baseline for each efficacy endpoint in Section 3.2.1 will be summarized by subgroup, ie, sex (male, female), ERT status (ERT naïve, ERT experienced), with descriptive statistics at each scheduled time point based on the enrolled population. Mean plots including standard error bars at each visit for the numerical observed values and changes from baseline of the indicated laboratory assessments, ECHO results and subject questionnaires will be provided by sex (male, female), ERT status (ERT naïve, ERT experienced), and overall, if feasible.

7.1. Laboratory Assessments

Efficacy analyses will include summaries of observed and change from baseline values for eGFR, urine protein, and urine albumin for scheduled visits by subgroup, ie, sex (male, female), ERT status (ERT naïve, ERT experienced), indicated in Section 4.6. By-visit summary will also include the last post-baseline values.

The eGFR will be calculated using the 2009 Schwartz formula for creatinine clearance.

A by-subject listing will be presented for each laboratory test.

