2. SYNOPSIS

Name of Sponsor/Company:

Amicus Therapeutics (Amicus)

Name of Investigational Product:

Migalastat hydrochloride (HCl)

Name of Active Ingredient:

Migalastat

Title of Study:

A Long-term, Open-label Study to Evaluate the Safety, Pharmacodynamics, and Efficacy of Migalastat in Subjects > 12 Years of Age with Fabry Disease and Amenable *GLA* Variants

Study Centers: Global, multicenter

Protocol Number: AT1001-036

Studied Period:	Phase of Development:
Estimated date first subject enrolled: Fourth quarter 2019	Phase 3b
Estimated date last subject completed: Second quarter 2022	

Objectives:

Primary

 to assess the long-term safety of migalastat treatment in pediatric subjects diagnosed with Fabry disease and who have variants in the gene encoding α-galactosidase A (α-Gal A) (*GLA*) amenable to treatment with migalastat

Secondary

- to characterize the pharmacodynamics (PD) of migalastat in pediatric subjects diagnosed with Fabry disease and who have *GLA* variants amenable to treatment with migalastat
- to assess the efficacy of migalastat in pediatric subjects diagnosed with Fabry disease and who have *GLA* variants amenable to treatment with migalastat

Methodology:

This is a long-term, open-label, uncontrolled, multicenter study to evaluate the safety, PD, and efficacy of migalastat treatment in subjects over 12 years of age with Fabry disease and with amenable *GLA* variants. Subjects will enroll in this study following completion of migalastat Study AT1001-020.

Enrollment in this study should immediately follow completion of Study AT1001-020 in order to maintain the continuity of treatment. As appropriate, assessments performed at the End of Treatment visit for Study AT1001-020 will be utilized for Visit 1 (baseline) assessments for this study.

Subsequent visits for this study will be scheduled every 6 months with interim telephone contacts at intervening 3-month intervals in order to monitor safety. In general, subjects must have completed Study AT1001-020 to be eligible for enrollment in this study. However, subjects who withdrew from that study for a reason not related to the safety or efficacy of migalastat may be eligible to participate in this study upon approval by the Amicus medical monitor.

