7.2. Duration of Treatment

Subjects will continue on the study until the date of regulatory approval or marketing authorization for pediatric patients with Fabry disease and availability of reimbursed product in the participating subject's country, or study termination by Amicus. Since subjects will be entering this study as they complete Study AT1001-020, the duration of treatment will vary among subjects.

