8.3. Withdrawal Criteria

8.3.1. Reasons for Discontinuation/Withdrawal

Subjects may discontinue study drug, withdraw from the study, or be withdrawn from the study for any reason including, but not limited to, the following reasons:

- at their own request or at the request of their parent or legally-authorized representative
- if, in the investigator's opinion, continuation in the study would be detrimental to the subject's well-being
- occurrence of an intolerable AE as determined by the investigator, subject, and/or parent or legally-authorized representative
- failure of the subject to comply with the study visit schedule
- persistent noncompliance, at the discretion of the investigator
- pregnancy
- subject becomes eligible for reimbursed product
- inability to contact subject (ie, subject is lost to follow-up)
- Amicus medical monitor request

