3.1. Summary of Study Design

This is a long-term, open-label, uncontrolled, multicenter study to evaluate the safety, PD, and efficacy of migalastat treatment in subjects over 12 years of age with Fabry disease and with amenable GLA variants. Subjects will enroll in this study following completion of migalastat Study AT1001-020.

Enrollment in this study should immediately follow completion of Study AT1001-020 in order to maintain the continuity of treatment. As appropriate, assessments performed at the End of Treatment visit for Study AT1001-020 will be utilized for Visit 1 (baseline) assessments for this study.

In order to monitor safety, subsequent visits for this study were initially scheduled every 3 months with monthly interim telephone contacts. Following Amendment 2, the visit schedule was changed to every 6 months, with phone contacts at intervening 3-month intervals.

Subjects will remain on the same dose of migalastat that they were receiving in Study AT1001-020. If a subject's weight decreases to below 43 kg, an unscheduled visit will be arranged 2 to 4 weeks later in order to monitor the subject's weight.

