5.6.1.5. Visit Windows

There will be no derivation for visit windows in terms of summary assessments. Nominal visits will be used for by-visit tables. For data with repeated observations at a given visit (eg, laboratory assessments), the earliest of the available non-missing values at a visit should be used in summary tables. Other observations will be considered as unscheduled visits.

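### The last post-baseline row for eGFR and LVMi averages changes over unequal follow-up, shows no time to the last value, and no rate of change is planned

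*SAP*

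**What the plan says.** Protocol 7.2 sets no fixed treatment length. A subject stays until paediatric approval and "availability of reimbursed product in the participating subject's country, or study termination by Amicus". It adds: "Since subjects will be entering this study as they complete Study AT1001-020, the duration of treatment will vary among subjects". Protocol 8.3.1 lists, among the reasons for leaving, "subject becomes eligible for reimbursed product".

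SAP 5.6.1.4 defines change from baseline as a simple difference between the visit value and the baseline value, not divided by time. SAP 7.1 summarises eGFR, urine protein and urine albumin as observed value and change at scheduled visits, by sex and ERT status, and states: "By-visit summary will also include the last post-baseline values". SAP 7.2 has the same provision for echocardiogram results. Visits are nominal (SAP 5.6.1.5: "There will be no derivation for visit windows in terms of summary assessments"), and Protocol 11.4 has data summarised as observed, without imputation.

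Neither Protocol 11.4.6 nor SAP 7 to 7.2 plans a slope, an annualised change or a longitudinal model. The SAP does adjust for exposure elsewhere: SAP 9.2 divides adverse event counts by patient-years.

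**The concern.** Protocol 5.1 describes Fabry disease as progressive, and Protocol 5.3.2.1 cites stable renal function over the long term in earlier adult studies. Whether kidney function or left ventricular mass is stable over unequal follow-up is a question about rate.

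The last post-baseline row is the one that takes in every subject with any later value, so it is the row most likely to be quoted as the overall result. It gives equal weight to a change over a few months and a change over more than two years. Because it is also split by sex and ERT status, a reader may take a gap between two groups for a difference in disease course when one group was simply followed for longer.

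LVMi is the more exposed endpoint. Echocardiograms are scheduled only at baseline, Months 12 and 24, and EOT/ET. A subject who leaves before Month 12 can contribute a scheduled post-baseline echocardiogram only through EOT/ET or the last-value row.

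**Working it through.** The documents give no sample size, expected change or variability, so there is no planned figure to reproduce. The slopes, follow-up patterns and residual SD below are assumptions. Months are 30 days, as the protocol defines them.

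**1. How far follow-up can range.** The protocol synopsis gives "Estimated date first subject enrolled: Fourth quarter 2019" and estimates last completion in the second quarter of 2022.
- Shortest span: 31 Dec 2019 to 1 Apr 2022 = 822 days; 822/365.25 = 2.25 years; 822/30 = 27.4 months.
- Longest span: 1 Oct 2019 to 30 Jun 2022 = 1003 days; 1003/365.25 = 2.75 years; 1003/30 = 33.4 months.

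On these dates, last values could fall anywhere from Month 6 (or earlier, at an early termination visit) to about Month 27 to 33 for the first subjects enrolled.

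**2. Last-value change at one common slope.** Change = slope × months × 30/365.25.

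| Assumed slope (mL/min/1.73 m2 per year) | Month 6 | Month 12 | Month 24 | Month 30 |
|---|---|---|---|---|
| -1 | -0.49 | -0.99 | -1.97 | -2.46 |
| -2 | -0.99 | -1.97 | -3.94 | -4.93 |
| -5 | -2.46 | -4.93 | -9.86 | -12.32 |

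The ratio of Month 30 to Month 6 is 30/6 = 5 at any non-zero slope. At slope 0 every entry is 0.

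**3. Two subgroups with the same slope.** Assume group A is followed 6, 6, 12 and 12 months (mean 9) and group B 18, 24, 24 and 30 months (mean 24). At -2 per year the row shows -2 × 9 × 30/365.25 = -1.48 in A and -2 × 24 × 30/365.25 = -3.94 in B, a ratio of 24/9 = 2.67. An annualised rate returns -2 in both.

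**4. By-visit rows.** Here nominal time is fixed. Assume 20 subjects, of whom 10 leave after Month 12, with an average slope of -2:

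| Slope: stayers / leavers | Month 6 | Month 12 | Month 18 | Month 24 |
|---|---|---|---|---|
| -2 / -2 | -0.99 | -1.97 | -2.96 | -3.94 |
| -1 / -3 | -0.99 | -1.97 | -1.48 | -1.97 |
| -3 / -1 | -0.99 | -1.97 | -4.44 | -5.91 |

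The trend is undistorted when leavers and stayers decline alike. It bends only when they differ.

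**5. Precision of per-subject slopes.** SE = SD/√Sxx, where Sxx is the sum of squared deviations of the measurement times in years. Assume a residual SD of 8 and half-years of exactly 0.5.
- Two values, 0 and 6 months: Sxx = 0.125, SE = 22.6 per year.
- Three values, 0, 6 and 12 months: Sxx = 0.5, SE = 11.3 per year.
- Five values, 0 to 24 months: Sxx = 2.5, SE = 5.06 per year.

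For an unweighted mean of slopes, counting residual error only:
- Five subjects at 6 months and five at 24: √[(5 × 22.6² + 5 × 5.06²)/100] = 5.2 per year.
- The five 24-month subjects alone: 5.06/√5 = 2.3 per year.
- Five subjects at 12 months and five at 24: √[(5 × 11.3² + 5 × 5.06²)/100] = 2.8 per year.

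Short slopes dominate an unweighted mean, so a 6-month minimum is too low.

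**The case against.** The strongest reply is that this concerns one supplementary row in a descriptive, uncontrolled study. The by-visit rows have a fixed time base and report n (SAP 5.4.1), the endpoint is change from baseline, and nothing is tested. Listings carry visit date and days from first dose (SAP 5.2), exposure duration is summarised (SAP 9.1), and anyone could compute a rate later. Protocol 5.4 also says renal involvement is less common at younger ages, so the slope may be near zero and the artefact negligible.

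Much of this stands. It confines the point to the last-value row and to interpretation. But a listing is not a summary, exposure duration is not time to the last eGFR or echocardiogram, and SAP 9.1 does not plan exposure by sex or ERT status. A rate chosen after the data are seen is weaker than one specified beforehand.

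A reader might infer more than the documents support:
- *That by-visit rows are also confounded with time on study.* They are not. Their limit is changing composition, which matters only if leavers differ from stayers. Exit follows country-level access, and nothing shows that this is related to prognosis.
- *That EOT/ET values drop out of the tables.* EOT/ET has its own column in the schedule, and SAP 5.6.1.5 does not exclude it.
- *That Months 3 and 9 hold laboratory values only from the former schedule.* SAP 3.1 says "Following Amendment 2, the visit schedule was changed to every 6 months", from 3-monthly visits, but not which tests those visits included. SAP 9.4 names Months 3 and 9 for vital signs only, and in the current schedule they are telephone contacts.
- *That follow-up reaches three years, or that the sexes or ERT groups were followed for different lengths.* The estimated span is about 2.25 to 2.75 years, and no subgroup follow-up is reported.

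**Conclusion.** The point holds for the last post-baseline row of eGFR and LVMi, overall and by sex and ERT status. Its size depends on time on study as well as on disease course, the time is not shown, and no planned summary of these endpoints expresses change per unit of time. With identical disease course, last values at Month 6 and Month 30 differ five-fold: about 2, 4 and 10 mL/min/1.73 m2 apart at assumed slopes of -1, -2 and -5 per year. The difference shrinks to nothing as the slope nears zero. No equivalent figure is offered for LVMi, because the documents give no basis for one.

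These figures run from Day 1 of AT1001-036, the SAP baseline. If the AT1001-020 baseline in Protocol 11.4 applies, each interval lengthens by that subject's time in the earlier study. For subjects with equal time there, the ratio falls but the absolute difference stays the same.

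This limits how the efficacy results can be read. It does not invalidate the by-visit tables and affects no error rate. The correction is worth making before database lock.

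**What to change.** 1. Reconcile the efficacy baseline. Protocol 11.4 takes it from the AT1001-020 baseline visit; SAP 5.5 takes the last value on or before the first dose in AT1001-036. State also whether AT1001-020 values enter any slope.
2. In SAP 7.1 and 7.2, keep the by-visit rows and the last-value row. Beside the latter, print the median and range of time from baseline to last value, in each column.
3. For eGFR and LVMi, add a descriptive annualised rate of change on actual dates, using all on-treatment values including EOT/ET and unscheduled ones, overall and by sex and ERT status.
   - If numbers allow, use a random-intercept, random-slope model, which gives short series less weight.
   - Otherwise summarise per-subject least-squares slopes (n, mean, SD, median, range) only for subjects with at least 12 months between first and last value, and report how many are excluded. Let the threshold allow for the 6-day visit window (12 × 30 − 6 = 354 days), so that an on-time Month 12 visit is not lost.
4. Print n under each visit on the mean plots.

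The cost is SAP wording and one table per endpoint, with no new data and no testing. The downside is imprecision: slopes from few subjects stay noisy, LVMi has at most three scheduled echocardiograms by Month 24 apart from EOT/ET, and the 12-month rule leaves out early leavers, who still appear in the by-visit and last-value rows.

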7.2. Echocardiography

A summary table of observed and change from baseline values in numerical ECHO results will be provided at each scheduled visit by subgroup, ie, sex (male, female), ERT status (ERT naïve, ERT experienced). By-visit summary will also include the last post-baseline values.

A by-subject listing will be presented for each ECHO parameter, including LVMi measurement, and other cardiac parameters, such as ejection fraction, fractional shortening, left ventricular internal diameter end diastole and end systole, midwall fractional shortening, and wall thickness.

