9.2.2.7. Echocardiogram

Echocardiogram parameters considered for safety include left ventricular mass index (LVMi), ejection fraction, fractional shortening, left ventricular internal diameter end diastole and end systole, midwall fractional shortening, and wall thickness.

Echocardiograms will be read centrally.

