9.2.4. Efficacy Assessments

9.2.4.1. Estimated Glomerular Filtration Rate

Estimated GFR will be calculated using the Schwartz formula according to the standards of the central laboratory. Subjects who reach the age of 18 and remain on study will continue to have eGFR calculated by this method by the sponsor at the time the value is entered into the database.

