11.4.4.7. Echocardiograms

Echocardiogram parameters (other than LVMi) will be summarized using descriptive statistics.

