2.2. Study Endpoints

2.2.1. Efficacy Endpoints

The efficacy endpoints of this study are as follows:

- change from baseline in estimated glomerular filtration rate (eGFR; Schwartz formula)
- change from baseline in urine protein and albumin levels
- change from baseline in left ventricular mass index (LVMi)
- change from baseline in Fabry-Specific Pediatric Health and Pain Questionnaire (FPHPQ) scores
- change from baseline in Pediatric Quality of Life Inventory[™] (PedsQL[™])

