2.2.3. Safety Endpoints

The safety endpoints of this study are as follows:

- incidence of treatment-emergent adverse events (TEAEs), serious adverse events (SAEs), and adverse events (AEs) leading to discontinuation of study drug
- change from baseline in clinical laboratory test results over time
- change from baseline in vital signs over time
- change from baseline in physical examination findings over time
- change from baseline in body weight and height over time
- change from baseline in electrocardiogram (ECG) results over time

- change from baseline in echocardiogram (ECHO) parameters from baseline to Month 12/ET
- change from baseline in Tanner stage

3. Study Design

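### Wall thickness and LV diameters are summarised without body-size adjustment in an uncontrolled study that includes growing adolescents, and the LVMi divisor is not stated

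*SAP*

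**What the plan says.** - **Analysis.** SAP 7.2: "A summary table of observed and change from baseline values in numerical ECHO results will be provided at each scheduled visit by subgroup", the subgroups being sex and ERT status. A row for the last post-baseline value is added, and the introduction to SAP section 7 adds mean plots of observed values and changes. Protocol 11.4.4.7 is equally brief: "Echocardiogram parameters (other than LVMi) will be summarized using descriptive statistics".
- **Parameters.** Besides LVMi, ejection fraction and fractional shortening, Protocol 9.2.2.7 lists "left ventricular internal diameter end diastole and end systole, midwall fractional shortening, and wall thickness".
- **Role.** SAP 2.2.1 lists "change from baseline in left ventricular mass index (LVMi") as an efficacy endpoint, and Protocol 9.2.4.3 makes LVMi the key echo parameter for efficacy. SAP 2.2.3 lists as a safety endpoint "change from baseline in echocardiogram (ECHO) parameters from baseline to Month 12/ET".
- **Population and design.** SAP 3.1: "This is a long-term, open-label, uncontrolled, multicenter study", evaluating "migalastat treatment in subjects over 12 years of age with Fabry disease and with amenable GLA variants". There is no upper age limit, and Protocol 9.2.4.1 provides for "Subjects who reach the age of 18 and remain on study".
- **Body size.** Height and weight are scheduled at every visit that has a scheduled echocardiogram (Protocol Table 2: baseline, Months 12 and 24, EOT/ET). They are reported in their own tables (SAP 9.4) and are not linked to the echo analysis.

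Neither document mentions a z-score, a paediatric reference or a size adjustment for the linear parameters, and neither defines the divisor of LVMi.

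**The concern.** Wall thickness and internal diameters increase as a body grows, with no disease or drug effect. A control arm would let growth be subtracted, but there is none. The plan itself expects growth and puberty, because height, weight and Tanner stage are safety endpoints. A mean rise in wall thickness could therefore reflect growth, disease or both, and a modest real fall could be offset. SAP section 1 says the planned analyses will go into regulatory submissions or manuscripts, so the means will be read as results.

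Three features of the plan make the growth component harder to separate:

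- Protocol 11.4 promises summaries by age group at baseline. The SAP's efficacy subgroups are sex and ERT status only, which drops the stratifier that would partly separate faster from slower growers.
- Protocol 11.4 takes the efficacy baseline from the AT1001-020 baseline visit, while SAP 5.5 uses Day 1 of AT1001-036. The length of growth inside each change score is therefore unsettled.
- Treatment duration varies by subject (Protocol 7.2), so the last post-baseline row pools different amounts of growth.

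**Working it through.** The plan gives no expected echo change, standard deviation, sample size or growth data, so there is no figure to reproduce. What follows is a sensitivity calculation on stated assumptions.

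**Assumption.** Heart and body grow in proportion, with no disease or drug effect. For a weight ratio W:

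- length (wall thickness, diameters) and height scale as W^(1/3)
- body surface area (BSA) scales as W^(2/3)
- LV mass scales as W

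Only the ratio matters, so no starting weight is needed. Weight gains of 0% to 30% are assumed.

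**Step 1: growth alone.**

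- Linear parameters: W^(1/3) − 1
- LVMi per BSA: W / W^(2/3) − 1 = W^(1/3) − 1
- LVMi per height^2.7: W / W^0.9 − 1 = W^0.1 − 1
- LVMi per height^3: W / W − 1 = 0

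| Weight gain | Wall thickness, diameters | LVMi per BSA | LVMi per height^2.7 | LVMi per height^3 |
|---|---|---|---|---|
| 0% | 0% | 0% | 0% | 0% |
| 5% | +1.6% | +1.6% | +0.5% | 0% |
| 10% | +3.2% | +3.2% | +1.0% | 0% |
| 20% | +6.3% | +6.3% | +1.8% | 0% |
| 30% | +9.1% | +9.1% | +2.7% | 0% |

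Dividing by height to the first power would leave more: W^(2/3) − 1 = +19.1% at 30%.

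**Step 2: masking in wall thickness.** With a true proportional fall t, the observed change is (1 − t) × W^(1/3) − 1.

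- t = 5%: 0.95 × 1.032 − 1 = −1.9% at 10% weight gain; 0.95 × 1.063 − 1 = +1.0% at 20%; 0.95 × 1.091 − 1 = +3.7% at 30%. The sign turns at W = (1/0.95)^3 = 1.166, about 16.6% weight gain.
- t = 10%: 0.90 × 1.091 − 1 = −1.8% at 30%. The sign does not turn within the range.

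**Step 3: cross-check under a different assumption.** Let LV mass scale as height^2.7, BSA = √(height × weight / 3600), and take assumed growth from 155 cm/47 kg to 162 cm/53 kg.

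- Mass ratio: (162/155)^2.7 = 1.127
- BSA ratio: √(162 × 53 / (155 × 47)) = 1.086
- LVMi per BSA: 1.127 / 1.086 − 1 = +3.8%
- Linear parameters: 1.127^(1/3) − 1 = +4.1%

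The weight gain here is 53/47 − 1 = 12.8%, so the result fits between the 10% and 20% rows above. Under this assumption LVMi per height^2.7 would show no growth effect.

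**Step 4: after adjustment.** Under proportional growth, a correctly size-adjusted linear measure changes by 0% from growth alone.

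**The case against.** The strongest reply is that this is a descriptive extension study with safety as its primary objective and no p-values (SAP 5.4.3). Echo results are split by sex, height and weight changes are tabulated for the same subgroups (SAP 9.4), and all data are listed. A reader can therefore see growth beside the echo change. That limits the severity. It does not correct the echo means or plots, since a separate table of height cannot be subtracted from a mean wall thickness.

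Four stronger readings are tempting, and the documents do not support them:

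- *LVMi is a raw change.* It is an index by definition. What can be said is that the divisor is unstated. It may be fixed by the central echo reader in material outside these two documents.
- *Normal growth will be classified as hypertrophy or dilation.* The plan sets no echo threshold for either; the PCS criteria in SAP 9.3 and 9.4 cover laboratory values and vital signs. The risk lies in interpreting mean changes.
- *Every change spans a year or more of growth.* The EOT/ET echocardiogram can fall within a year of baseline.
- *Large growth is typical.* No growth data are given, and subjects near or past 18 may grow little or not at all.

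Ejection fraction and fractional shortening are ratios and are outside this point.

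**Conclusion.** The point holds for wall thickness and LV end-diastolic and end-systolic diameters. Their mean changes confound growth with disease and treatment effect. Under proportional growth the artefact is about 1.6% to 9.1% for 5% to 30% weight gain and nil in subjects who have stopped growing. That is enough to cancel or reverse a true fall of about 5%, but not a fall of 10% within this range.

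For LVMi the point is narrower. The divisor is missing from both documents, and on the same assumption the residual growth dependence at 30% weight gain runs from none (height cubed) to about 9% (BSA). A reader cannot tell which applies to the key cardiac efficacy measure.

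The percentages rest on assumed growth and are not estimates for this trial. The confounding itself follows from the design and the planned summaries. This is a worthwhile and inexpensive improvement; it does not invalidate the study's primary objective.

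**What to change.** In SAP 7.2:

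1. Derive body-size-adjusted z-scores for wall thickness and both LV diameters at every echocardiogram, using the height and weight from the same visit, and sex-adjusted where the reference allows. Z-scores for age alone would not do this, because they do not adjust for body size.
2. Prespecify one named reference for all visits. It must cover the full age and size range, including subjects who pass 18.
3. Summarise change in z-score beside the raw values, which stay in the tables and listings.
4. State the LVMi divisor and hold it constant at all visits, including values carried over from AT1001-020. If it is BSA, add a height-power-indexed value or an LV mass z-score.

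The cost is a few derived variables and one extra block per echo table, with no new measurement. The downside is that a reference has to be chosen, named and defended.
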